#### **9.4.8 Physical Examination**

Each infant physical examination will include the following physical observations: Length; Weight; Head Circumference; Vital Signs; General Appearance; Skin; Head, Ears, Eyes, Nose, and Throat (HEENT); Lymph Nodes; Heart; Lungs; Abdomen; Extremities/Joints; Neurological; Mental Status; and External Genitalia.

If clinically significant worsening of the physical examination assessments compared to Baseline is noted, the change will be documented as an AE on the AE CRF and will be followed as an AE consistent with the procedures outlined in [Section 9.4.1](#). Clinical significance is defined as any variation in physical findings that has medical relevance resulting in an alteration in medical care.

The infant's Apgar score will be determined at 1 minute and 5 minutes after birth.

#### **9.4.9 Developmental Assessment**

The Denver II Developmental Screening Test will be used as an evaluation tool for developmental abnormalities. The Denver II Developmental Screening Test is used to evaluate 4 developmental areas: personal-social, fine motor, language, and gross motor. Information regarding the Denver II Developmental Screening Test is provided in the SOM. If the assessment is abnormal, more in-depth testing will be undertaken based on the local standards of care.

#### **9.4.10 Genotype Testing**

Genotype testing will be conducted for all participating infants on umbilical cord blood to determine diagnosis of Fabry disease. Buccal cells will be collected from the mother by buccal swab to rule out contamination of the cord blood sample with maternal DNA (MCC analysis). The basic premise of the MCC test is the comparison of highly polymorphic short tandem repeat loci between the maternal and fetal DNA samples following polymerase chain reaction.

In cases when umbilical blood cord sample is not collected at the Baseline visit, genotyping of the infant enrolled for full participation could be performed on the additional blood sample collected at visit month 12. If genotyping of the infant is performed as a part of standard care prior to visit month 12, this result will be recorded by Investigator in the CRF.

Blood and buccal cell sample collection, processing, and shipping instructions are provided in the SOM.

#### **9.4.11 Immunogenicity Testing**

Immunogenicity testing will be conducted in those infants with parent(s)/legal guardian(s) consent. Blood collection, processing, and shipping instructions for infant blood samples for antibodies (IgG and IgM) to r-h $\alpha$ GAL are provided in the SOM.

#### **9.4.12 Safety Follow-Up**

Study sites will attempt to reach all study participants by telephone approximately 28 days after the final study procedures are completed, to conduct concomitant medication and adverse experience/event assessment.

## **10 DATA COLLECTION, QUALITY ASSURANCE, AND MANAGEMENT**

### **10.1 RECORDING OF DATA**

All required data will be recorded in the CRF provided by Genzyme. All missing data will be explained. If a space is blank because the item was not done, the item will be marked “ND.” If the item is unknown, the item will be marked “UNK.” If the item is not applicable to the individual case, the space will be marked “NA.” If the item is not available, it will be marked “NAV.” All entries will be recorded in black ink. Any erroneous entries made on the CRFs will be crossed out with a single line, initialed and dated, and the correct entry, if appropriate, will be recorded. Errors may not be erased and whiteout may not be used.

### **10.2 DATA QUALITY ASSURANCE**

The CRFs will be reviewed by a clinical monitor from Genzyme or designee for completeness and accuracy. Source document verification will be performed. The data will also be reviewed internally by Genzyme data management or designee and if necessary, the investigational sites will be queried for corrections and/or clarifications.

### **10.3 DATA MANAGEMENT**

The format and content of the CRF will be approved by Genzyme or designee prior to the start of the trial. Genzyme or designee will be responsible for database creation and management of data from other sources (eg, non-safety specialty lab data).

Prior to finalizing and locking the database, all decisions concerning the inclusion or exclusion of patient data for analysis will be determined by appropriate clinical and statistical personnel. Any exclusion will be documented. Protocol deviations will be tracked by Genzyme or its designee.

## **11 STATISTICAL METHODS AND PLANNED ANALYSES**

### **11.1 GENERAL CONSIDERATIONS**

Genzyme will be responsible for data entry and editing, reviewing all the information in the CRFs, statistical analysis, and generation of the clinical report.

Clinical data will be double-entered and validated in an Oracle database using Clintrial 4.5.

The Genzyme Biomedical Data and Informatics will perform the statistical analysis of the data derived from this study. The analysis will be performed using the SAS® statistical software system. (9)(10) The status of this study will be summarized annually as part of the Fabry Registry Program Annual Report.

Any missing or invalid data will not be replaced or imputed.

Data collected in this study will be reported using summary tables, graphs, figures, and/or patient data listings.

No hypothesis testing will be performed.

### **11.2 DETERMINATION OF SAMPLE SIZE**

No formal statistical sample size calculations were performed for this study. The sample size of approximately 10 mothers and up to 10 infants is based upon 1) the availability of mothers to study lactation in this rare disease and 2) the availability of infants whose parents or legal guardians consent to their participation in this study.

### **11.3 ANALYSIS POPULATIONS**

The patient populations will consist of all the mothers and all the infants who were enrolled in the study.

### **11.4 DEMOGRAPHICS AND BASELINE CHARACTERISTICS**

Demographic and Baseline characteristics data will be summarized for the mothers and for the infants.

### **11.5 PATIENT ACCOUNTABILITY**

Data from all patients who are enrolled in the study will be included in the summary of patient accountability. The frequency and percentage of patients who are enrolled in the study, attended each visit, are discontinued from the study, and completed the study will be summarized for the mothers and for the infants.

## **11.6 STUDY TREATMENT USAGE AND COMPLIANCE**

Not applicable.

## **11.7 EFFICACY ANALYSIS**

Not applicable.

## **11.8 SAFETY ANALYSIS**

The following study variables will be summarized as appropriate for the mothers:

- Medical history (including Fabrazyme status during pregnancy)
- Genotyping
- Pregnancy outcome
- IgG antibody status
- Lactation status
- Plasma and breast milk PK testing
- The level of  $\alpha$ GAL, volume, and fat and protein content in breast milk samples
- Frequency of AEs
- Frequency of concomitant medications

The following study variables will be summarized as appropriate for the infants:

- Medical history
- Physical examination
- Gender
- Genotype
- Apgar score at 1 minute and 5 minutes after birth
- Denver II Developmental Screening Test
- IgM antibodies to r-h $\alpha$ GAL – presence, time to development, level of titers present
- IgG antibodies to r-h $\alpha$ GAL – presence, time to development, level of titers present
- Frequency of AEs
- Frequency of concomitant medications

## 11.9 INTERIM ANALYSIS

After 5 mothers have contributed breast milk samples to this study, an interim analysis of  $\alpha$ GAL activity in the breast milk will be performed. [REDACTED]

In addition, the status of this study will be summarized annually as part of the Fabry Registry Program Annual Report and the Fabrazyme Post-Marketing Commitment Annual Report.

## 11.10 PHARMACOKINETICS ANALYSIS

Because of the limited sampling schedule, the only PK parameters that will be reported are maximum concentration ( $C_{max}$ ) and area under the plasma  $\alpha$ GAL concentration-time curve (AUC) from 0 to 2 hours post end of infusion ( $AUC_{0-2}$ ). A more complete PK profile is not being done because it is not the objective of the study to characterize the pharmacokinetics of  $\alpha$ GAL in lactating mothers.

Lactation clearance will be determined using the same calculations used to assess renal clearance. Breast milk will be collected at Baseline (sample 1) to empty each breast of milk, at end of infusion (sample 2), and 2 hours post-dose (sample 3). The amount of  $\alpha$ GAL will be calculated as the product of  $\alpha$ GAL activity times the milk volume. AUC from Baseline to 2 hours after the end of infusion will be calculated using a linear trapezoid. Lactation clearance will be estimated as the amount of  $\alpha$ GAL excreted over the sampling period divided by the AUC during the sampling period. The milk to plasma ratio calculated as the  $AUC_{milk}$  to  $AUC_{plasma}$  from time 0 (sample 2) to 2 hours after the end of infusion (sample 3) will also be computed.

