
CRITERIA FOR EVALUATION:
 
Mother
 
 
• Efficacy: Efficacy will not be measured in this study.
 
• Pharmacokinetics: Blood and breast milk samples will be taken from the mother at Months 1, 3, and 6 for measurement of αGAL concentrations (if mother is lactating at the time of the evaluation and is receiving Fabrazyme therapy). Blood samples will be collected prior to each breast milk collection as follows: sample 1: immediately prior to Fabrazyme infusion and prior to breast milk collection; sample 2: just prior to the end of Fabrazyme infusion and prior to breast milk collection; and sample 3: 2 hours after Fabrazyme infusion and prior to breast milk collection. Breast milk samples will be collected after each plasma collection for PK testing as follows: sample 1: immediately prior to Fabrazyme infusion and after plasma collection; sample 2: immediately after Fabrazyme infusion and after plasma collection; and sample 3: 2 hours after Fabrazyme infusion and after plasma collection. The volume of breast milk expressed from each timepoint (immediately prior to infusion, from infusion start until end of infusion, and from end of infusion until 2 hours post-infusion) will be recorded and summarized.
 
• Breast Milk: Samples of expressed breast milk will be collected by pump at Months 1, 3, and 6 (if mother is lactating at the time of the evaluation and continues to receive Fabrazyme therapy) for PK assessment as above. Additionally, the volume, fat content, and protein content of breast milk samples will be determined.
 
• Safety: The IgG antibody titers and incidence of adverse events (AEs) occurring in mothers enrolled in this study will be summarized.
 
 
Infant
 
 
• Efficacy: Efficacy will not be measured in this study.
 
• Immunoglobulins: At birth, a sample of umbilical cord blood will be collected to determine the infant's Baseline anti-r-hαGAL IgM and IgG titers. Testing for presence of IgG and IgM antibodies will also occur at Month 2, 6, and 12.
 
• Development: The infant's growth and development will be monitored from birth to Month 24 through physical exams and the Denver II Developmental Screening Test.
 
• Safety: The incidence of adverse events occurring in infants enrolled in this study will be summarized.
 
 
Genotype testing: will be conducted for all participating infants on umbilical cord blood to determine diagnosis of Fabry disease. In cases when umbilical blood cord sample is not collected at the Baseline visit, genotyping of the infant enrolled for full participation could be performed on the additional blood sample collected at visit month 12. If genotyping of the infant is performed as a part of standard care prior to visit month 12, this result will be recorded by Investigator in the CRF (Case Report Form).
		

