### Pharmacokinetic parameters

The following pharmacokinetic parameters will be calculated, using noncompartmental methods from plasma  $\alpha$ GAL concentrations and milk  $\alpha$ GAL concentrations

- maximum plasma concentration observed ( $C_{max}$ ) in plasma and milk
- area under the plasma  $\alpha$ GAL concentration versus time curve calculated using the trapezoidal method from 0 to 2 hours post end of infusion ( $AUC_{0-2 \text{ plasma}}$ ).

- The amount of  $\alpha$ GAL in milk calculated as the product of  $\alpha$ GAL activity times the milk volume
- area under the milk  $\alpha$ GAL concentration versus time curve calculated using the trapezoidal method from 0 to 2 hours post end of infusion ( $AUC_{0-2 \text{ milk}}$ ).
- Lactation clearance determined in the 0-2 hours interval, according to the following equation : amount of  $\alpha$ GAL excreted over the sampling period divided by the AUC during the sampling period

The milk to plasma ratio for  $AUC_{0-2}$  will also be computed.

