#### **9.4.7 Breast Milk Samples**

Breast milk samples of mothers receiving Fabrazyme will be tested for  $\alpha$ GAL activity, volume, and fat and protein content. Since  $\alpha$ GAL is a protein, it is a normal component of breast milk and it is possible that the women enrolled in the study naturally produce  $\alpha$ GAL in the breast milk samples. The current assay cannot differentiate between endogenous  $\alpha$ GAL and Fabrazyme. As breast milk samples are not available prior to the mother having started Fabrazyme therapy, breast milk samples will be tested just prior to the Fabrazyme infusion and at timed intervals as specified above (see [Section 9.3](#)) to see if there is an increase in the  $\alpha$ GAL levels in breast milk.

Each breast milk collection should first be measured for total volume. An aliquot of each breast milk sample collected at the site is to be set aside for testing and the remainder of the sample may be fed to the infant. Refer to the SOM for further details on breast milk sampling.

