2.1.5 Pharmacokinetic variables

Pharmacokinetic Sampling

α GAL concentrations will be measured from Blood and breast milk samples taken from the mothers. Blood samples will be taken from the mother at Months 1, 3, and 6 for PK testing (if mother is lactating at the time of the evaluation and is receiving Fabrazyme therapy).

Bioanalytical Method

Plasma and milk α GAL concentrations will be quantified by measuring enzyme activity using a fluorometric assay with a lower limit of quantification of 1.38 ng/mL. The assay does not differentiate between endogenous α GAL and Fabrazyme.

Pharmacokinetic parameters

The following pharmacokinetic parameters will be calculated, using noncompartmental methods from plasma α GAL concentrations and milk α GAL concentrations

- maximum plasma concentration observed (C_{max}) in plasma and milk
- area under the plasma α GAL concentration versus time curve calculated using the trapezoidal method from 0 to 2 hours post end of infusion ($AUC_{0-2 \text{ plasma}}$).
- the amount of α GAL in milk calculated as the product of α GAL activity times the milk volume
- area under the milk α GAL concentration versus time curve calculated using the trapezoidal method from 0 to 2 hours post end of infusion ($AUC_{0-2 \text{ milk}}$).

- lactation clearance determined in the 0-2 hours interval, according to the following equation: amount of α GAL excreted over the sampling period divided by the AUC during the sampling period

The milk to plasma ratio for AUC₀₋₂ will also be computed.

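### Lactation clearance has two different intervals in the documents, and milk AUC0-2 treats interval collections as time points, so the numerator of the milk to plasma ratio does not match its plasma divisor

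*Protocol*

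**What the plan says.** **How milk is collected.** Protocol 11.10 has milk taken at sample 1 "to empty each breast of milk, at end of infusion (sample 2), and 2 hours post-dose (sample 3". The synopsis (Criteria for Evaluation) records expressed volume for three periods: "immediately prior to infusion, from infusion start until end of infusion, and from end of infusion until 2 hours post-infusion". Protocol 9.4.7 adds: "Each breast milk collection should first be measured for total volume"; an aliquot is then set aside for testing.

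**Milk AUC0-2 and the ratio.** Protocol 9.3 and SAP 2.1.5 apply the same rule to plasma and to milk: a "concentration versus time curve calculated using the trapezoidal method from 0 to 2 hours post end of infusion". Protocol 11.10 fixes the sample times for the ratio: "from time 0 (sample 2) to 2 hours after the end of infusion (sample 3) will also be computed".

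**Lactation clearance.** All three sections divide the amount excreted over the sampling period by the AUC over that period, but the period differs. Protocol 11.10 says "AUC from Baseline to 2 hours after the end of infusion will be calculated using a linear trapezoid"; Baseline here is sample 1, taken just before the infusion, not the pre-delivery study visit. Protocol 9.3 says "Lactation clearance determined in the 0-2 hours interval", and SAP 2.1.5 says the same. No section states which milk samples supply the amount. The AUC meant is the plasma one: 11.10 defines it as the plasma "concentration-time curve (AUC) from 0 to 2 hours post end of infusion".

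SAP 1.6 lists no statistical modification, so the SAP does not settle the difference.

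**The concern.** Two programmers could follow the documents faithfully and report different lactation clearances. Pairing the amount from samples 2+3 with the 0-2 h AUC would be a third possibility, and it would mismatch numerator and denominator.

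The ratio has a different problem. If the breasts are emptied at sample 1 and all the milk of each collection is measured before the aliquot is drawn, then C2 is an average over infusion-period milk and C3 an average over the next 2 h. Neither is a concentration at an instant. Protocol 11.10 recognises this for clearance, where it uses the renal-clearance calculation and multiplies activity by volume. For the ratio it places the same samples at 0 and 2 h as points. The numerator then depends on infusion length and on the delay between plasma and milk, so the ratio can vary between mothers and visits for reasons unrelated to how much enzyme passes into milk.

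**Working it through.** The documents give no AUC, clearance, infusion length, half-life or transfer rate, so there is no planned figure to reproduce. Steps 1 and 2 are exact; steps 3 to 5 rest on assumptions.

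**1. Milk AUC0-2.** Planned: 2 h x (C2 + C3)/2 = 1 h x C2 + 1 h x C3. Interval-matched: 2 h x C3. Planned / matched:

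F = (1 + C2/C3)/2

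The coefficient weight on sample 2 is exactly one half. Its share of the AUC value is C2/(C2 + C3), which depends on the data:

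| C2/C3 (assumed) | F | Share of value from sample 2 |
|---|---|---|
| 0.1 | 0.55 | 9% |
| 0.5 | 0.75 | 33% |
| 1 | 1.00 | 50% |
| 2 | 1.50 | 67% |

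The two methods agree only when C2 = C3.

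**2. Clearance.** With milk amounts A2 and A3:

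- 0-2 h version: A3 / AUC0-2.
- Pre-infusion to 2 h version: (A2 + A3) / (AUC over infusion + AUC0-2).

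They agree only if A2/A3 equals the plasma AUC over the infusion divided by AUC0-2.

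**3. Size under assumed kinetics.** One-compartment infusion of length T = 1.5, 2, 3, 4 or 6 h; plasma half-life 0.75, 1, 1.5 or 2 h; plasma-to-milk equilibration half-life 0.25, 0.5, 1 or 2 h; constant milk flow; 5 x 4 x 4 = 80 scenarios.

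One scenario traced: T = 3 h, plasma half-life 1.5 h (rate 0.462/h), equilibration half-life 1 h (rate 0.693/h), plasma plateau scaled to 1.

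- Plasma at end of infusion: 1 - 2^(-3/1.5) = 0.75. At 2 h: 0.75 x 2^(-2/1.5) = 0.298. Linear AUC0-2 = 0.75 + 0.298 = 1.048. Infusion segment = 3 x 0.75/2 = 1.125.
- C2 = 1 - [1.5 x 0.75 - 0.667 x 0.875]/(0.231 x 3) = 0.219.
- After the infusion, milk follows 2.25e^(-0.462t) - 1.75e^(-0.693t); its 2 h average is C3 = 0.522.
- F = (1 + 0.219/0.522)/2 = 0.71.
- Clearance, 0-2 h: 2 x 0.522/1.048 = 0.996. Pre-infusion to 2 h: (3 x 0.219 + 2 x 0.522)/(1.125 + 1.048) = 1.701/2.173 = 0.783. Second over first: 0.79.

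Across the 80 scenarios:

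- F runs from 0.61 (T = 1.5, half-life 2, equilibration 2) to 1.14 (T = 6, half-life 0.75, equilibration 0.25), median 0.76. It exceeds 1 in 5 scenarios.
- The second clearance version over the first is 0.71 to 1.35.

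**4. Endogenous activity.** Protocol 9.4.7 says the enzyme is a normal component of milk and that the assay cannot separate it from drug. A constant endogenous level of e x drug-derived C3 gives F' = 1 + (F - 1)/(1 + e).

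- e = 1: from 1 - 0.39/2 = 0.805 to 1 + 0.14/2 = 1.07.
- e = 3: from 1 - 0.39/4 = 0.90 to 1 + 0.14/4 = 1.04. No scenario is beyond 10%. The clearance versions then differ by 0.98 to 1.27.

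**5. Does the interval-matched ratio do better?** The linear plasma trapezoid overstates AUC0-2 by 4% to 27% in this model, which lowers both ratios. Against the model's true ratio:

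| | Range | Median |
|---|---|---|
| Planned | 0.51-0.90 | 0.68 |
| Interval-matched | 0.79-0.96 | 0.90 |

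The matched version is closer in 75 of 80 scenarios. It is still closer in 75 of 80 with 20% or 50% of infusion-period milk left behind at sample 2, but at 50% it falls to 0.59-0.92 of truth (median 0.73). With instant plasma-milk equilibration (20 further scenarios), two errors partly cancel and the planned ratio is closer in 11 of 20.

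**The case against.** The milk AUC0-2 rule is not a contradiction. Protocol 9.3, protocol 11.10 and SAP 2.1.5 agree on it, it can be programmed, and 11.10 says sampling is limited and that characterising pharmacokinetics is not an objective. That stands: on this half the point is about the choice of estimator.

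Emptying is stated only for sample 1. Using sample 3 alone assumes near-complete emptying at sample 2, and sampling detail is left to the Study Operations Manual, which is not available here. That also stands and must be written into any fix. It does not rescue the planned rule, because incomplete emptying would not turn sample 2 into a time-0 reading.

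The clearance conflict might be read away by taking 0 as the start of infusion in 9.3 and the SAP. Protocol 11.10 itself puts time 0 at sample 2, and the other two name a 0-2 h interval, so the natural reading leaves the conflict. The synopsis leaves analysis details to the SAP, which favours 0-2 h, but the milk amount remains undefined.

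A reader might go further and infer that the planned ratio is biased by a known amount, that sample 3 alone is the correct basis for clearance, or that a log trapezoid is needed for plasma. The documents support none of these. They give no kinetic values. Both clearance versions are internally valid once amount and AUC match, and samples 2+3 start from the only emptying that the protocol states. The benefit of a log rule depends on an assumed shape of decline.

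**Conclusion.** The concern holds on two counts. The clearance interval in protocol 11.10 conflicts with that in protocol 9.3 and SAP 2.1.5, and the milk amount is unspecified; this needs no kinetic model to establish. The milk AUC0-2 gives half its coefficient weight to milk collected over the infusion, against a post-infusion plasma divisor; the error factor (1 + C2/C3)/2 is exact, given interval collection.

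The sizes (0.71-1.35 for clearance, 0.61-1.14 for the milk AUC) rest wholly on assumed kinetics and constant milk flow. The milk AUC error could go either way and could be small if endogenous activity is high. Consequences are confined to two descriptive pharmacokinetic quantities in about 10 mothers, with no hypothesis test. Objective 1 is unaffected, as are per-sample activity, volume and amount; a reader should not infer that the finding on the presence of enzyme in milk is compromised. The point is worth fixing because the fix costs little, not because the stakes are high.

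**What to change.** - **Clearance.** Reconcile protocol 9.3, protocol 11.10 and SAP 2.1.5 to one interval, with milk amount and plasma AUC over the same period: either sample 3 amount / plasma AUC0-2, or samples 2+3 amount / plasma AUC from pre-infusion to 2 h. Report the other as a sensitivity analysis. Either is acceptable as the main version; samples 2+3 have the advantage of starting from the stated emptying at sample 1.
- **Milk to plasma ratio.** Calculate milk AUC0-2 as sample 3 concentration x the actual collection interval (about 2 h). State that this assumes near-complete emptying at sample 2 and roughly constant milk flow. Show the planned trapezoid version alongside.
- **Plasma rule.** State one trapezoid rule for plasma AUC. Protocol 11.10 says linear for the pre-infusion to 2 h AUC; protocol 9.3 and SAP 2.1.5 do not say which.

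The cost is wording in three sections and one or two formulas on samples already planned, using actual infusion-end and collection times. No new procedure is needed.
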